4.0 Risk/Benefit Assessment

4.1 Risks and Anticipated Adverse Events:

Risks: This study is considered to entail minimal risk for study subjects because topical corticosteroids are routinely used off label to prevent cornea transplant rejection.

A number of complaints and complications are anticipated in patients who have received a cornea transplant, regardless of whether they participate in this study. Therefore, the presence or absence of the following anticipated complaints and complications in the study eye will be recorded on the electronic case report form (eCRF) for each exam rather than on separate adverse event forms.

- Complaints of ocular discomfort: (examples include: eye pain, irritation, burning, itching, scratchy feeling, foreign body sensation, tired/fatigued feeling, achy/tender/sore feeling, pressure sensation, tightness, twinge/twitchy feeling, dry eyes, tearing/watering, eye redness)
- Complaints of visual symptoms or disturbances: (examples include: glare or fluctuating vision, haloes around lights, diplopia, blurry, hazy, cloudy, filmy or out of focus vision, ghosting or shadowing, difficulty reading, difficulty with night driving, floaters, spots in vision, light sensitivity, decreased vision, light reflections from intraocular lens or peripheral iridotomy).
- Increased ptosis (within the first 6 months of surgery)

- Puffy eyelids (within the first 3 months of surgery)
- Delayed resolution of corneal haze or edema (within the first 6 months of surgery)
- Subconjuntival hemorrhage (within the first 3 months of surgery)
- Epithelial defect (within the first month of surgery)
- Folds in the transplant
- Partial graft detachment without further intervention
- Development of capsular haze without further intervention
- Superficial punctate keratitis
- Pupillary block (within the first 3 months of surgery)

Adverse events: The type, severity, duration and frequency of the following anticipated adverse experiences and any other unanticipated ocular adverse events will be tabulated. If a patient experiences an adverse reaction, appropriate medical treatment will be provided. Examples may include:

- Graft detachment which requires intervention
- Immunologic graft rejection episode
- Graft failure and/or regraft
- Intraocular pressure elevation which requires intervention
- Development of capsular haze which requires intervention
- Iris synechia
- Cystoid macular edema
- Iritis

Anticipated rare adverse events include retinal detachment, iris synechiae/atrophy, epiretinal membrane, infectious keratitis or conjunctivitis, branch retinal vein occlusion, or endophthalmitis.

Serious Adverse Event: A serious adverse event is one that results in any of the following outcomes: death, a life-threatening adverse event, inpatient hospitalization or prolongation of existing hospitalization, a persistent or significant disability/ incapacity, or a congenital anomaly/birth defect. In the event of a serious adverse event, the investigator will maintain complete documentation and promptly inform the governing Institutional Review Board (IRB) of the serious adverse event within their required reporting period.

Fellow eye: Each subject may enroll one eye into the study. Patients in this population tend to be affected with the eye condition bilaterally, so many of the study subjects may undergo surgery on the fellow eye during the year of study participation. Routine fellow-eye post-transplant complications will not be transcribed to the eCRF.

4.2 Protection Against Risks: Every effort will be made to minimize any risks or discomforts to study subjects. The investigator will ensure appropriate training of study personnel and monitoring of subjects and will provide appropriate treatment for eye-related adverse events or referral for treatment of non-eye-related adverse events. The subject and or their health insurance plan will be responsible for payment for treatment, counseling or follow up.

A Data Safety Monitoring Committee (DSMC) will be chaired by [name], an independent ophthalmologist practicing in Menasha, Wisconsin. The DSMC will review any serious adverse events as they occur. The DSMC will also review the interim data (including adverse events and subject compliance) every 6 months, to determine if any modifications to the original study plan may be warranted. Urgent data and safety monitoring reports (e.g. reports indicating an unanticipated problem involving risk) will be reported to the IRB within 10 business days of the Sponsor receipt of the report. Routine reports will be submitted to the IRB with the Sponsor's Study Status Report.

- **4.3 Potential Benefits to the Subjects:** Study subjects may not realize any direct benefit from participation in the research; rather, important knowledge which may benefit future subjects is being sought.
- **4.4 Study termination:** The study may be prematurely terminated if, in the opinion of the investigator or the Sponsor, there is sufficient reasonable cause. Written notification, documenting the reason for study termination, will be provided to the investigator or Sponsor by the terminating party. Circumstances that may warrant termination include, but are not limited to:
 - Determination of unexpected, significant, or unacceptable risk to subjects.
 - Insufficient adherence to protocol requirements.
 - Data that is not sufficiently complete or evaluable.
 - Plans to modify, suspend or discontinue marketing of the Study Product.

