- Records release: Subjects may be asked to sign a records release form in case the subject_sees another eye specialist while enrolled in the study. This will allow the investigator to determine if there is a rejection episode or elevated intraocular pressure at examinations made with other physicians. Since the primary and secondary outcome measures (slit lamp examination for evidence of rejection and intraocular pressure measurement) are routine ophthalmic exams, the subject may have some of the exams performed by a local eye doctor if getting back to the study site is too burdensome.

- O Unscheduled examinations: Subjects will be instructed to return for extra examinations if they note any problems with the eye or any early signs of a possible rejection episode, such as a change in vision, redness to the eye, increased light sensitivity, burning sensation, or foreign body sensation.
- o Study completion: Subjects will be considered to have completed the study after they complete the one-year postoperative examination.
- Subject withdrawal or discontinuation: Each subject may voluntarily discontinue the study at any time they choose. Subjects who cannot complete the study for administrative reasons (e.g., non-compliance, failure to meet visit schedule, etc.) will be discontinued from the study. Discontinued subjects may be replaced. For subjects withdrawn from the study, the same measurements and assessments should be performed as done at one year. Adverse events should be followed up until resolution or stabilization of the adverse event.

Table 1

| | Screening | 3 months | 6 months | One year |
|--------------------------|-------------|------------|----------|----------|
| | (∼1 month | after DMEK | after | after |
| | after DMEK) | | DMEK | DMEK |
| Informed Consent | X | | | |
| Inclusion/Exclusion | X | | | |
| Criteria | | | | |
| Medical and | X | X | X | X |
| ophthalmic history | | | | |
| Adverse Events | | X | X | X |
| Uncorrected visual | X | X | X | X |
| acuity (Snellen) | | | | |
| Corrected Distance | X | X | X | X |
| visual acuity (Snellen) | | | | |
| Manifest refraction | X | X | X | X |
| Endothelial cell density | X | X | X | X |
| (if possible) | | | | |
| Intraocular Pressure | X | X | X | X |
| Ultrasonic Pachymetry | X | X | X | X |

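### Section 4.1 keeps ocular discomfort, visual symptoms and punctate keratitis off adverse event forms without limit, so local tolerability of loteprednol 0.25% is under-described

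*Combined protocol and SAP*

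**What the plan says.** Section 4.1 of the protocol has two recording rules.

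The first covers problems expected after a transplant whether or not the patient takes part in the study. For these, the entry for the study eye is a yes or no, which "will be recorded on the electronic case report form (eCRF) for each exam rather than on separate adverse event forms". The list has 12 entries. One begins "Complaints of ocular discomfort: (examples include: eye pain, irritation, burning, itching, scratchy feeling, foreign body sensation" and goes on to include "dry eyes, tearing/watering, eye redness". Another covers visual symptoms, among them "light sensitivity, decreased vision, light reflections from intraocular lens or peripheral iridotomy". Superficial punctate keratitis is a separate entry. None of these three has a time limit. Other entries do, for example "Pupillary block (within the first 3 months of surgery").

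The second rule covers adverse events: "The type, severity, duration and frequency of the following anticipated adverse experiences and any other unanticipated ocular adverse events will be tabulated". Its examples include graft rejection, graft failure, iritis and intraocular pressure (IOP) elevation that needs intervention.

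Section 3.1 (unscheduled examinations) tells patients to come back for an extra exam if they notice problems or possible early signs of rejection, "such as a change in vision, redness to the eye, increased light sensitivity, burning sensation, or foreign body sensation".

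**The concern.** The reason given for the first rule is that these problems follow the surgery. That is sound for surgical recovery. It does not cover a complaint that was absent at enrolment and first appears after the switch to loteprednol 0.25%. Burning, irritation, redness and punctate keratitis are the kind of local effect by which poor tolerance of an eye drop would show, and for these entries the exemption never ends.

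The study's stated purpose is to assess an off-label use of this drop. If a patient returns early because of burning, or stops the drop because of it, a reader of the adverse event table should be able to see when it began, how severe it was and how it ended. Under 4.1 as written that information is not called for.

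**Working it through.** The plan gives no figure to reproduce here. The check compares the two lists in 4.1 with each other and with 3.1.

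**Step 1. Limits on the 12 exempt entries.** Inputs: the list in 4.1; study drug from about month 1 after surgery to the month 12 exam (3.1), so 12 − 1 = 11 months. For a patient who starts the drop at month 1, the months on study drug covered by each exemption are the end of the window minus 1.

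| Entries | Limit in 4.1 | Exempt months on study drug |
|---|---|---|
| Epithelial defect | 1 month | 1 − 1 = 0 |
| Puffy eyelids, subconjunctival hemorrhage, pupillary block | 3 months | 3 − 1 = 2 |
| Ptosis, delayed clearing of haze or edema | 6 months | 6 − 1 = 5 |
| Partial graft detachment, capsular haze | only if no intervention | 11, while untreated |
| Ocular discomfort, visual symptoms, punctate keratitis, graft folds | none | 11 |

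The count is 1 + 3 + 2 = 6 entries with a time limit, 2 with an intervention limit and 4 with neither: 6 + 2 + 4 = 12. Setting aside ocular discomfort, visual symptoms and punctate keratitis, 8 of the other 9 entries have a limit. Graft folds are the exception.

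**Step 2. Match with 3.1.** Change in vision, redness, light sensitivity, burning and foreign body sensation all fall within the two exempt complaint groups (5 of 5). Punctate keratitis is not among the signs in 3.1. So the plan treats these symptoms as reason enough for an extra exam, but the complaint itself goes on the checklist.

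**Step 3. Other routes to a fuller record.**

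- *A diagnosis.* If the exam shows rejection, iritis or IOP elevation needing intervention, that event is tabulated with severity and duration. This route works.
- *The catch-all.* It reaches only ocular events that were not anticipated. These complaints are declared anticipated.
- *Timing from the checklist.* Onset is known to the exam. Scheduled exams at months 1, 3, 6 and 12 leave gaps of 3 − 1 = 2, 6 − 3 = 3 and 12 − 6 = 6 months; an unscheduled exam narrows the gap.
- *Slit lamp.* Section 3.1 has hyperemia, punctate keratitis and other surface toxicity documented at each exam, but states no grading scale, and symptoms are not part of it.
- *Follow-up to resolution or stabilization.* Section 3.1 requires this for adverse events. A complaint on the checklist does not trigger it.

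What is left over is a listed complaint, or punctate keratitis, that first appears on study drug and is not attributed to a named or unanticipated adverse event. It gets a visit-level yes or no. No rule in 4.1 moves it to an adverse event form, whatever followed from it.

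**The case against.** The rule is deliberate and its reason is stated. Many of the listed complaints, such as floaters, tired eyes or difficulty reading, are common background in these patients, and a form for each would bury the useful events. Tolerability is not an outcome: the planned comparison with the earlier studies concerns rejection and ocular hypertension. The adverse event list is introduced as examples, so an investigator could file a form anyway. The safety committee reviews interim data in general, not only adverse event forms.

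Much of this stands. It argues against a form for every new or worse complaint, the more so because a yes/no checklist gives no baseline severity against which to judge worsening. It does not explain why discomfort, visual symptoms and punctate keratitis have no limit when most of their neighbours do. Leaving it to the investigator's discretion also runs against the explicit instruction to use the checklist instead of the form.

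A reader might infer several stronger points that the documents do not support:

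- *That such problems are never graded or dated.* They are dated to the exam, including unscheduled exams, and those that lead to a named diagnosis are recorded with severity and duration.
- *That early under-protection goes unseen.* Section 3.2 makes rejection, or a steroid increase for breakthrough inflammation, a primary outcome with Kaplan-Meier analysis, and rejection and iritis are also adverse events.
- *That 3.1 treats punctate keratitis as a sign of rejection.* It does not name it.
- *That pupillary block must move to the adverse event list.* An IOP rise needing intervention is an adverse event whatever its cause, and IOP that meets the threshold in 3.2 counts toward the primary outcome. The overlap loses no IOP data.

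**Conclusion.** The point holds as a limited gap in safety recording. Three of the 12 exempt entries, those that would carry most of the local tolerability information, are kept off adverse event forms for all of the roughly 11 months on study drug, with no time or intervention limit. A complaint of this kind that prompts an extra exam or stopping of the drop is recorded without severity, onset date or outcome unless it is attributed to another event. The adverse event table will therefore under-describe local tolerability.

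The gap does not affect the two primary outcomes or the power statement in 3.2. How many patients it would touch cannot be estimated, because the documents give no complaint rates; the ceiling is the enrolment limit of 75. The conclusion assumes that the site follows 4.1 literally and that the case report form holds no severity or onset field beyond what the protocol describes.

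**What to change.** Amend 4.1 to use the split by consequence that it already applies to graft detachment, capsular haze and IOP elevation. A listed complaint, or punctate keratitis, that was absent at the enrolment exam and leads to an unscheduled exam, to a change or stopping of the study drop, or to treatment is also entered on an adverse event form with onset date, severity and outcome. All other listed complaints stay on the presence/absence checklist. From that checklist, tabulate complaints new since enrolment, by exam, for the 6-monthly review by the Data Safety Monitoring Committee.

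This needs the checklist to be completed at the enrolment exam. Section 4.1 calls for it at each exam, but Table 1 has no row for it and its adverse event row starts at 3 months, so the amendment should say so explicitly. Using absence at enrolment as the test avoids any need for a baseline severity.

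The cost is amended wording, one extra table for the committee, a longer adverse event table and some extra forms. The number of forms should be small because the trigger is narrow, but the documents give no rate from which to calculate it. The change concerns recording only and alters nothing in treatment.

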5.0 Method of Subject Identification and Recruitment

5.1 Process of Consent The process of obtaining the consent consists of explaining the eye condition and explaining the risks and benefits of the proposed treatment and alternatives. In addition, the patient will be allowed to read the consent and ask questions prior to signing the informed consent form. The patient may take home an unsigned copy of this consent form to think about or discuss with family or friends before making a decision.

Study coordinators, who have been trained in obtaining consent by the investigator and who have experience in consenting subjects for clinical trials, will obtain informed consent. Consent will be obtained in a private exam room with the door closed to protect the privacy of participants. The study will be explained to participants and if subjects have specific questions which the study coordinator cannot address, the principal investigator will be available to answer the questions.

- **5.2 Subject Capacity:** All subjects will be evaluated for capacity to consent through the use of the Cornea Research Foundation of America Evaluation to Sign a Consent Form. Any subjects who do not answer the Evaluation questions satisfactorily will be considered cognitively impaired and will not be enrolled into the study as they would not meet the study's inclusion/exclusion criteria.
- **5.3 Subject/Representative Comprehension:** Subjects will be given time to ask any questions, and study information will be explained until it is clear that all information presented is understood.
- **5.4 Debriefing Procedures:** Not applicable; this is not a psychological study and no information will be purposely withheld from the subject.

6.0 Consent Forms

- **6.1 Documentation of Consent** Patient's medical records and informed consent documents will be maintained and stored with access limited to the authorized personnel. All research records will be kept separate and locked with limited access by research personnel only.
- **6.2 Costs to the Subject:** The subject and or their health insurance plan will be responsible for payment for treatment, counseling or follow up.

6.3 Payment for Participation: Subjects will be provided with the assigned topical corticosteroid for the duration of the study. Subjects will not receive any payment for study participation.

